9.2.2 Continuous Endpoints

Mixed-Effect Model Repeat Measurement (MMRM) will be the primary approach to handle missing data for continuous endpoints. The MMRM will be conducted using mixed model including observed measurements at all visits, using all available data even if a subject has missing data at some post-baseline visits. The mixed model includes the fixed effects of categorical variables of treatment, actual stratification factors (Baseline BSA category and Baseline ppIGA category), visit and treatment-by-visit interaction at all post-baseline visits in each Study Period, and the continuous variable of Baseline measurement as covariates. Subjects' observations after discontinued study drug due to lack of efficacy will be excluded from the model. An unstructured variance covariance matrix (UN) will be used. If the model cannot converge, an appropriate covariance structure matrix (e.g., autoregressive (1) or compound symmetry) will be used. The parameter estimations are based on the method of restrictive maximum likelihood (REML). The fixed effects will be used to report model-based means at corresponding visits.

Of note, during the Primary Analysis upon completion of Week 16, the MMRM analysis will only be performed at all visits up to Week 16.

Long-term efficacy in the Period 2 will be summarized using the observed case approach.

Observed Case (OC): The OC analysis will be used for the summaries of long-term efficacy in Period 2, which will use observed data.

9.3 Primary Efficacy Endpoint and Analyses

9.3.1 Primary Efficacy Endpoint

The primary efficacy endpoint is the achievement of ppIGA of 0 or 1 with at least a 2-point reduction from Baseline at Week 16 as defined in Section 3.1.

9.3.2 Main Analysis of Primary Efficacy Endpoint

The following null hypothesis corresponding to the primary endpoint will be tested under a two-sided significance level of 0.05:

- There is no difference between risankizumab and placebo, with respect to the proportion of subjects achieving ppIGA of 0 or 1 with at least a 2-point reduction from Baseline at Week 16.

The primary endpoint will be analyzed among the ITT Population, using the Cochran-Mantel-Haenszel (CMH) test adjusting for the actual values of stratification factors.

The attributes of the estimand corresponding to the primary efficacy endpoint are summarized in Table 2.

Table 2. Summary of the Estimand Attributes of the Primary Efficacy Endpoint

Estimand Label	Attributes of the Estimand				
	Treatment	Endpoint	Population	Handling of Intercurrent Events	Statistical Summary
ppIGA 0 or 1 at Week 16	Risankizumab 150 mg / Placebo	Achievement of ppIGA 0 or 1 with a least 2-point reduction from Baseline at Week 16	ITT	Subjects who discontinued study drug due to lack of efficacy prior to Week 16 will be considered as non-responders.	Difference in proportion of subjects achieving ppIGA 0 or 1 with a least 2-point reduction from Baseline at Week 16 between risankizumab 150 mg and placebo

Comparison will be made between risankizumab and placebo using the CMH test, adjusting for the actual values of stratification factors (Baseline ppIGA and Baseline BSA categories). NRI-C will be the primary approach to handle missing data.

9.3.3 Sensitivity and Supplementary Analyses of the Primary Efficacy Endpoint

A sensitivity analysis using MI to handle missing data will be performed on the primary endpoint, as defined in Section 9.2.1. Treatment, Baseline BSA, and the observed ppIGA assessments at all Baseline and post-baseline visits will be included in the imputation model.

9.4 Secondary Efficacy Endpoints and Analyses

9.4.1 Key Secondary Efficacy Endpoints

The ranked secondary endpoints are as defined in Section 3.2.

9.4.2 Main Analyses of Key Secondary Efficacy Endpoints

The following null hypotheses pertaining to the ranked secondary efficacy endpoints will be tested between the risankizumab and placebo groups among the ITT Population in a hierarchical order, only if the null hypothesis for the primary endpoint has been rejected:

1. There is no difference between risankizumab and placebo, with respect to the proportion of subjects achieving PPASI 75 at Week 16
2. There is no difference between risankizumab and placebo, with respect to the proportion of subjects achieving PPASI 90 at Week 16
3. There is no difference between risankizumab and placebo, with respect to the proportion of subjects achieving sPGA of "clear" or "almost clear" (0 or 1) with at least a 2-point reduction from Baseline at Week 16
4. There is no difference between risankizumab and placebo, with respect to the proportion of subjects achieving PPASI 100 at Week 16

Ranked secondary endpoints will be analyzed, using the CMH test adjusting for the actual values of stratification factors. NRI-C will be the primary approach to handle missing data.

The attributes of the estimands corresponding to the ranked secondary efficacy endpoints are summarized in [Table 3](#).

Table 3. Summary of the Estimand Attributes of the Ranked Secondary Efficacy Endpoint

Estimand Label	Attributes of the Estimand				
	Treatment	Endpoint	Population	Handling of Intercurrent Events	Statistical Summary
PPASI 75 at Week 16	Risankizumab 150 mg / Placebo	Achievement of PPASI 75 at Week 16	ITT	Subjects who discontinued study drug due to lack of efficacy prior to Week 16 will be considered as non-responders.	Difference in proportion of subjects achieving PPASI 75 at Week 16 between risankizumab 150 mg and placebo
PPASI 90 at Week 16	Risankizumab 150 mg / Placebo	Achievement of PPASI 90 at Week 16	ITT	Subjects who discontinued study drug due to lack of efficacy prior to Week 16 will be considered as non-responders.	Difference in proportion of subjects achieving PPASI 90 at Week 16 between risankizumab 150 mg and placebo
sPGA 0 or 1 at Week 16	Risankizumab 150 mg / Placebo	Achievement of sPGA 0 or 1 with a least 2-point reduction from Baseline at Week 16	ITT	Subjects who discontinued study drug due to lack of efficacy prior to Week 16 will be considered as non-responders.	Difference in proportion of subjects achieving sPGA 0 or 1 with a least 2-point reduction from Baseline at Week 16 between risankizumab 150 mg and placebo
PPASI 100 at Week 16	Risankizumab 150 mg / Placebo	Achievement of PPASI 100 at Week 16	ITT	Subjects who discontinued study drug due to lack of efficacy prior to Week 16 will be considered as non-responders.	Difference in proportion of subjects achieving PPASI 100 at Week 16 between risankizumab 150 mg and placebo

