2.3 Treatment Assignment and Blinding

All subjects will be assigned a unique identification number by the interactive response technology (IRT) system at the screening visit. For subjects who rescreen, the screening number assigned by the IRT at the initial screening visit should be used. The IRT will assign a randomization number that will encode the subject's treatment group assignment according to the randomization schedule generated by Data and Statistical Sciences (DSS) at AbbVie.

Subjects will be centrally randomized at the Baseline visit in a 1:1 ratio to receive either SC risankizumab 150 mg or matching placebo during Period A, and all subjects will receive open label risankizumab 150 mg once every 12 weeks during Period B. Randomization will be stratified by Baseline ppIGA ("moderate" [3] versus "severe" [4]) and Baseline body surface area (BSA) affected (< 10% versus \geq 10%).

All AbbVie personnel with direct oversight of the conduct and management of the study (with the exception of AbbVie Drug Supply Management Team) will remain blinded until the Primary Analysis at Week 16 is available. The investigator, study site personnel, and the subject will remain blinded to each subject's treatment throughout the study. To maintain the blind, the risankizumab pre-filled syringe (PFS) and placebo PFS provided for the study will be identical in appearance.

In the event of a medical emergency in which the investigator believes that knowledge of study drug treatment is required, reasonable efforts must be made to contact the AbbVie emergency contact prior to breaking the blind, as long as it does not compromise subject safety. However, if an urgent therapeutic intervention is necessary which warrants breaking the blind prior to contacting the AbbVie emergency contact, the investigator can directly access the IRT system to break the blind without AbbVie agreement. The date

and reason that the blind was broken must be recorded in the source documentation and electronic case report form (eCRF), as applicable.

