2.4 Sample Size Determination

The ppIGA is an endpoint that has been used in another clinical trial in the palmoplantar psoriasis population and which is based on the modified Investigator's Global Assessment version of 2011.^{1,2} Given the lack of historical ppIGA data from risankizumab trials, the assumption of response rates in the current study are based on the relevant endpoints of PPASI 75 and PPASI 90 from risankizumab PsO Studies M15-992, M15-995, and M16-008, among subjects who had Baseline PPASI of at least 8. Among these subjects, approximately 80% and 75% of subjects from the risankizumab (RZB) group achieved PPASI 75 and PPASI 90, respectively; compared to 50% and 40% in the placebo (PBO) group.

Assuming that 75% of subjects from the RZB group and 45% of subjects from the PBO group would achieve the primary endpoint of ppIGA of 0 or 1 with at least a 2-point reduction from Baseline at Week 16, the sample size of 168 subjects (84 subjects per group) will provide more than 90% power to detect the treatment difference between RZB and PBO, under a 2-sided significance level of 0.05.

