9.0 Efficacy Analyses

9.1 General Considerations

All efficacy analyses will be conducted among the ITT Population. All statistical tests will be performed at a 2-sided alpha level of 0.05.

The Primary Analysis will be conducted after all continuing subjects complete Week 16 and all data pertaining to Period A are cleaned. This will be the only and final analysis for efficacy in Period A. Study sites and subjects will remain blinded to their initial treatment assignment for the duration of the entire study.

For categorical endpoints, comparisons will be made between risankizumab and placebo using the Cochran-Mantel-Haenszel (CMH) test, adjusting for the actual values of stratification factors (Baseline ppIGA and Baseline BSA categories). In case of any stratum with zero subject in either treatment group, no stratification factor will be controlled. Non-responder imputation (NRI) incorporating multiple imputation (MI) to handle missing data due to COVID-19 (NRI-C) will be the primary approach to handle missing values.

For continuous endpoints, comparisons will be made between risankizumab and placebo based on the fixed term of treatment from a Mixed-effect Model Repeat Measurement (MMRM) model including the Baseline value and observed measurements at all post-baseline visits, adjusting for the fixed effects of treatment, actual values of stratification factors, visit and treatment-by-visit interaction as covariates. The MMRM will be the primary approach to handle missing values.

"Baseline" refers to the last non-missing observation on or before the date of the first administration of study drug or the date of randomization if no study drug is administered. For variables where the assessment time is collected on the ePRO device, the baseline measurement must be prior to the time of the first administration of study drug.

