2.3 Imputation Algorithm

It is reasonable to assume the missing values of the longitudinal data for an outcome variable (e.g., PPASI, the original scale of PPASI 75, at each post-baseline visit) follows a monotone missing pattern. In practice, the missing data of the outcome variable might have an arbitrary (non-monotone) missing data pattern. An extra step may be added accordingly, to augment data into a monotone missing pattern.

For the outcome variable (e.g., PPASI at each visit), K 'complete' datasets can be generated in two steps: augmentation step and imputation step. K, the number of repetitions, is determined below.

Augmentation Step

For datasets with non-monotone missing data pattern, the augmentation step will first impute enough values to augment the data into a monotonic missing pattern:

Markov Chain Monte Carlo (MCMC) will be applied to augment the data using PROC MI with the MCMC IMPUTE=monotone statement, assuming a multivariate normal distribution. The augmented data will be used in the subsequent imputation step to generate 'complete' datasets. Covariates included in the model are treatment group, Baseline BSA, Baseline ppIGA category, Baseline (if other than Baseline ppIGA), and all post-baseline visits of the outcome variable up to the end of the Study Period. Of note, categorical variables are included using the form of dummy variables.

Repeat the imputation process K=30 times using the procedure described above to form K=30 monotone missing datasets, where K is determined as described in "Repetition of Imputations (K)."

Imputation Step

For missing data with monotone missing patterns, the choice of multiple imputation using a parametric regression model that assumes multivariate normality is appropriate.

The imputation step is described below:

- The imputation model for the missing data is a regression model, which controls for treatment group, Baseline BSA, Baseline ppIGA category, Baseline (if other than Baseline ppIGA), and all post-baseline visits of the outcome variable up to the end of the Study Period. The covariates included in the model and the order of these variables are consistent with the augmentation step.
- For each monotone missing dataset, using SAS PROC MI with MONOTONE REG model statement, the outcome variable at each post-baseline visit with missing values will be imputed sequentially with covariates constructed from their corresponding sets of preceding variables.

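### The CMH tests of the four ranked secondary endpoints are valid but do not adjust for the endpoint's own Baseline (PPASI or sPGA), which may forgo some precision, mainly for sPGA 0/1 and PPASI 100

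*SAP*

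**What the plan says.** SAP 9.4.2 covers PPASI 75, PPASI 90, sPGA 0/1 and PPASI 100 at Week 16: "Ranked secondary endpoints will be analyzed, using the CMH test adjusting for the actual values of stratification factors". SAP 9.1 names the factors: "adjusting for the actual values of stratification factors (Baseline ppIGA and Baseline BSA categories"). Appendix E 2.5 repeats them for the analysis of each imputed dataset. SAP 9.4.3 plans no sensitivity or supplementary analysis for these endpoints.

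Own Baseline is used elsewhere in the plan. The NRI-C imputation model (Appendix E 2.3) controls for "treatment group, Baseline BSA, Baseline ppIGA category, Baseline (if other than Baseline ppIGA), and all post-baseline visits of the outcome variable". For continuous endpoints, the MMRM in SAP 9.2.2 includes Baseline ppIGA and BSA categories "and the continuous variable of Baseline measurement as covariates". Protocol 7.4 likewise adds the baseline value to the MMRM unless it would duplicate a stratification factor.

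The other categorical endpoints (SAP 9.5) get the same CMH analysis on the stratification factors alone.

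**The concern.** For the primary endpoint, the ppIGA stratum is the outcome's own Baseline. For the four ranked secondary endpoints, no stratum plays that role. A prognostic baseline variable that is left out of the analysis leaves variance in the treatment comparison that could have been removed at no cost in subjects.

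The endpoints are tested in a fixed order, and SAP 2.4 states power only for the primary. The third and fourth tests, sPGA 0/1 and PPASI 100, have neither a stated power nor an assumed response rate. What is at stake is interval width on all four endpoints and perhaps some power on the last two. The validity of the tests is not in question.

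**Working it through.** **Inputs from the documents.** 84 per group, 1:1, two-sided alpha 0.05 (SAP 2.3, 2.4, 9.1). Rates in SAP 2.4: primary 75% vs 45%; PPASI 75 80% vs 50%; PPASI 90 75% vs 40%. **Assumed, because the documents give nothing:** rates for sPGA 0/1 and PPASI 100, and the prognostic strength of own Baseline.

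**1. Reproduce the stated power.** Power = Φ{[|p1−p2|√n − 1.96√(2p̄(1−p̄))] / √(p1(1−p1)+p2(1−p2))}. For 75% vs 45%, p̄ = 0.60 and n = 84: (2.750 − 1.358)/0.660 = 2.11, so power is 98.3%. This agrees with the stated figure of more than 90%.

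**2. PPASI 75 and PPASI 90.** The same formula gives 98.7% and 99.8%. The most that adjustment could add is 1.3 and 0.2 points. For PPASI 75 the standard error is √[(0.80×0.20 + 0.50×0.50)/84] = 0.070, a 95% half-width of 13.7 points. With 13% less variance the half-width is 13.7 × √0.87 = 12.8 points.

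**3. How far each definition already carries Baseline.** PPASI 75 and 90 scale by the subject's own Baseline. PPASI 100 means a Week 16 PPASI of zero whatever the Baseline, and entry values can run from 8 (Protocol 5.1) up to the scale maximum of 72 (Appendix E 2.2). For sPGA, entry requires a score of at least 3, so reaching 0 or 1 already implies a 2-point drop. A subject starting at 4 must improve by 3 points, one starting at 3 by 2. Own Baseline therefore has most room to matter for sPGA 0/1 and PPASI 100.

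**4. Variance removed (assumed prognostic strength).** Simulation with n = 168, 2,000 trials per setting, moderate response rates; reduction = 1 − 1/ratio.

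| Odds ratio per SD | Unadjusted/adjusted variance | Reduction |
|---|---|---|
| 1 | about 1.00 | 0% |
| 0.74 | 1.00-1.03 | 0-3% |
| 0.55 | 1.04-1.05 | 4-5% |
| 0.37 | 1.13-1.15 | 12-13% |

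A second simulation used linear adjustment, with own Baseline correlated 0.5 with the severity underlying ppIGA. It gave adjusted/CMH standard-error ratios of about 1.00, 0.99-1.00, 0.97-0.98 and 0.92-0.96 for the same four strengths. Squared, the last is a reduction of 8-15%. A 13% reduction is worth 168/0.87 = 193, or about 25 extra subjects.

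**5. Power at assumed rates.** Replace n by 84/(1 − reduction).

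| Assumed rates | 0% | 5% | 10% | 13% |
|---|---|---|---|---|
| 40% vs 20% | 81.3 | 83.3 | 85.2 | 86.4 |
| 25% vs 10% | 72.9 | 75.1 | 77.4 | 78.8 |
| 30% vs 10% | 90.7 | 92.1 | 93.4 | 94.1 |

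The gain is about 0-5 points, with 5.9 in the most favourable cell. Direct simulation gives less. At 40% vs 20%, against the Mantel-Haenszel risk-difference test of Appendix E, power moved from 83.3% to 82.5%, 84.2% to 85.9%, and 85.7% to 89.4% for odds ratios of 0.74, 0.55 and 0.37. The first change is no gain: with 3,000 trials, one such power has a Monte Carlo standard error of √(0.83×0.17/3000) = 0.7 points. At 30% vs 10%, linear adjustment reached at most 93.8%, from about 92% with CMH.

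**6. Covariate or extra stratum.** Splitting the CMH strata further at the Baseline median gave standard-error ratios of 1.01-1.02 with no prognostic value and only 0.96-0.98 at the strongest. Extra strata would also make the SAP 9.1 rule that drops all stratification more likely to apply. A model covariate adds no strata.

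**The case against.** The strongest case against acting is that nothing is wrong. A CMH analysis on the randomisation factors matches the design and is a standard choice. It already adjusts for Baseline ppIGA, a related palmoplantar severity score. Eligibility restricts Baseline sPGA to two levels. All of that stands.

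A reader might infer that the plan is inconsistent because own Baseline is dropped only from the error-controlled tests. The documents do not support this. SAP 9.5 applies the same CMH analysis to the additional categorical endpoints, so the plan divides by data type: CMH for categorical, MMRM for continuous. The MMRM comparison does not reach sPGA at all, since SAP 3.3 lists no continuous sPGA endpoint. Having Baseline in the imputation model supports the missing-at-random assumption and does not oblige the test to include it.

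Type I error is a fair worry. One null simulation gave 5.4-5.6% for standardised logistic regression, against 4.8-5.3% for CMH and 5.6-6.1% for the Mantel-Haenszel Wald form that Appendix E actually combines over imputations. Another gave 4.0-4.9% for the adjusted analysis at a 20% response rate. The adjusted analysis is thus no worse than the Appendix E form, but not clearly better than the CMH test itself. Model failures arose mainly at about 5% response, which is where PPASI 100 on placebo could lie. PPASI 100 is also last in the order, so failing it blocks no later test.

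**Conclusion.** The point holds as a modest efficiency improvement. Own Baseline PPASI or sPGA is collected but absent from the analysis of the ranked secondary endpoints. Adding it targets the same difference in proportions as SAP Table 3 and costs essentially nothing when Baseline is uninformative. Over assumed odds ratios per SD of 1 to 0.37, the variance falls by about 0-13% and power rises by about 0-5 points at assumed rates such as 40% vs 20% or 25% vs 10%. Any real benefit lies mainly with sPGA 0/1 and PPASI 100. For PPASI 75 and PPASI 90 it is at most a slightly narrower interval.

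Two stronger readings should be resisted. The tests do not ignore Baseline: the endpoints are defined relative to it and the strata carry related severity. Nor is a loss of precision on all four endpoints shown: with no prognostic value beyond the strata, nothing is lost, and the documents give no figure for that value.

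**What to change.** Only if the change is made before unblinding, whose date the documents do not give:

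- In SAP 9.4.2 and Appendix E 2.5, estimate each ranked secondary risk difference by standardised logistic regression with a robust standard error. Include treatment, Baseline ppIGA category, Baseline BSA category and own Baseline (log PPASI for PPASI 75/90/100; sPGA 3 vs 4 for sPGA 0/1). Combine over imputations by Rubin's formula.
- Keep ITT, NRI-C, the hierarchy and alpha unchanged. State how a subject with missing own Baseline enters the model, so that no one leaves the ITT set.
- Pre-specify an objective rule for using the planned CMH analysis instead, such as non-convergence or a minimum responder count pooled over arms. Report CMH as supportive in any case.

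If unblinding has occurred, leave the main test alone and report the adjusted estimate only as a supplementary analysis in SAP 9.4.3.

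The cost is SAP wording and a small amount of programming. The downside is a model-based estimator that may often revert to CMH if PPASI 100 responders are very few.

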9.4.3 Sensitivity and Supplementary Analyses for Key Secondary Efficacy Endpoints

Not applicable.

9.5 Additional Efficacy Analyses

Additional efficacy endpoints will be compared between the risankizumab and placebo treatment groups among the ITT Population at each visit in Period A.

Categorical endpoints will be analyzed, using the CMH test adjusting for the actual values of stratification factors. NRI-C will be the primary approach to handle missing data.

Continuous endpoints will be analyzed based on the fixed term of treatment from an MMRM model including the Baseline value and observed measurements at all post-baseline visits, adjusting for the fixed effects of treatment, actual values of stratification factors, visit and treatment-by-visit interaction as covariates.

Summary statistics will be provided for the additional efficacy endpoints at each visit in Period B by treatment groups. Categorical endpoints will be summarized by the number and proportion of subjects who achieved the endpoint, as well as the 95% confidence interval of that proportion. Missing data will be handled by NRI-C. Continuous endpoints will be summarized based on OC by descriptive statistics including the mean, standard error, and the 95% confidence interval of the mean.

